### 5.3. Safety Assessment

#### 5.3.1. Adverse Event

Assessments will be made on the adverse events (AEs) including any sign, symptom, disease or illness that occurred newly or if present at baseline, worsened in a subject and may impair the well-being of the subject. Clinical laboratory findings and any other findings from the diagnostic procedures that are considered clinically significant (e.g. requiring unscheduled diagnostic procedures or treatment modalities or resulting in discontinuation of the study) will also be included in the AE assessment.

AEs will be collected and evaluated at each visit after informed consent is signed until 28 calendar days after the last administration of the investigational product. Any AEs that emerged following administration of IP will be evaluated in comparison to the baseline level of AEs determined at screening.

See [Section 7](#) for detailed information on **SAFETY REPORT** of this study.

### 5.3.2. Clinical Laboratory Tests

The following tests will be performed locally at individual investigational sites. Hematology, chemistry, coagulation and urinalysis will be performed at Day 1 (before IP administration) and Day 15 of every cycle, the end of treatment (EOT) visit and the post-  
tx F/U visit. If hematological or non-hematological treatment related toxicity occurs, laboratory tests can be performed at the investigator's discretion during the treatment period. Serological tests will be performed only at the screening visit and additional tests can be performed as clinically indicated or as required by local health authorities.

- Hematology (complete blood count, CBC: white blood cell (WBC) with 5-part differential (neutrophils, lymphocytes, monocytes, eosinophils, and basophils), platelet count, absolute neutrophil count (ANC), red blood cell count (RBC), hemoglobin (Hb), hematocrit (Hct)
- Blood chemistry: sodium, potassium, chloride, carbon dioxide or bicarbonate (if required), blood urea nitrogen (BUN), creatinine, glucose (fasting), total protein, albumin, calcium, amylase, lipase, phosphorous, magnesium, creatinine kinase (CK), uric acid, total bilirubin, AST, ALT, and ALP
- Serological tests: HIV antibody (if HIV antibody result is positive, HIV-1 antibody and HIV-2 antibody should be conducted), HBs antigen, HBs antibody, HBC antibody, HCV antibody
- Coagulation tests: prothrombin time expressed as either prothrombin time (PT) or international normalized ratio (INR) and partial thromboplastin time (PTT or aPTT)
- Urinalysis: specific gravity, protein, glucose, occult blood, and microscopic examination if indicated
- Pregnancy test: it will be carried out only for female subjects with child-bearing potential (serum or urine).

### 5.3.3. Vital Signs and Physical Findings

Body temperature (oral, axillary, core, temporal, or tympanic), blood pressure (systolic/diastolic), heart rate, and respiratory rate will be collected as vital signs. Vital signs will be measured at every visit with the subject in a sitting position at rest for at least 5 minutes. Systemic physical examination will be performed within 14 days before the date of randomization and at every study visit thereafter.

### 5.3.4. Weight and Height

Weight (kg) will be measured at each visit and height (cm) will be measured only at the screening visit.

### 5.3.5. Eastern Cooperative Oncology Group Performance Status

ECOG Performance Status (refer to [Appendix 1](#)) will be assessed at every visit.

### 5.3.6. ECG Monitoring

A 12-lead ECG should be performed within 14 days before the date of randomization, at Day 1 of every cycle (before IP administration), at EOT visit and at the post-treatment follow-up visit. In addition, a 12-lead ECG should be performed approximately 4 hours after IP administration on Cycle 1 Day 1 and Cycle 1 Day 15. Additional ECG should be performed as clinically indicated. Any abnormal findings in ECG measurements with clinical significance should be reported as adverse events.

To facilitate the safety analysis in [section 8.3.7](#) of the ECG data, if approved by country and local regulatory authorities, duplicate copies (either digital or hard copies) of the ECG tracing and the evaluation report should be transferred to the Sponsor after de-identifying the subject information for further clinical evaluation of ECG data as per regulatory recommendations. The original ECG results will be kept on file at the site as source documentation. Handling of this information/data will be done in accordance with the applicable data protection laws. (US government CFR 21 Part 11 for electronic records; US government Health Insurance Portability and Accountability Act (HIPPA), etc.)

As the request for the ECG copies is during an amendment, it is typically necessary to either ensure that informed consent is obtained to facilitate submittal of these ECG copies to the sponsor (or sponsor representatives) or in the case where consent cannot be updated (i.e. subject has expired), appropriate local ethics committee approval is obtained to authorize the submittal of these ECG copies.

### 5.3.7. Chest X-Ray

A chest x-ray should be performed as clinically indicated. Any abnormal findings in chest x-ray measurements with clinical significance should be reported as adverse events.

## 5.4. Exploratory Assessment

### 5.4.1. Pharmacodynamic (PD) marker

At baseline, all subjects will be tested for Single-Nucleotide Polymorphisms (SNPs) to identify genotypes associated with the response to therapy with VEGFR-2 inhibitor.

Vascular Endothelial Growth Factor (VEGF) will be evaluated at;

- The 1st day of 1st cycle
- The 1st day of 2nd cycle and each cycle thereafter (prior to IP administration)
- End of Treatment visit

In addition, plasma samples for sVEGFR-1, sVEGFR2 and sVEGFR3 will be taken.

Guidelines for collection and handling of blood specimen and materials will be provided by the sponsor or sponsor's designee. Each study site collects and ships the specimens to the central laboratory according to the guidelines provided.

Genetic test will be conducted including the gene information that specifies the patient and will be used only for research purpose. Therefore, the results of genetic test will not be disclosed to the patient, patient's family, investigators, or other third parties and will not be recorded in the patient's medical record.

In Japan, if the patient is under 20 years old and the patient or legal guardian withdraws consent, the collection and sampling of blood sample will be stopped. However, the information and blood samples already collected and sampled can be used to evaluate the result of the clinical trial.

### 5.4.2. Biological Sample Storage

The sponsor may wish to analyze blood samples in the future for the research purpose. Blood samples will be tested and stored for up to 10 years after the end of the study and then destroyed, unless other time limitations are required by local regulations or ethical requirements. Samples should be frozen at site and will be shipped to the sponsor or its designee during or at the end of the study as requested by the sponsor.

### 5.4.3. Tumor Biopsy

The sponsor may wish to analyze tumor biopsy samples in the future for the research purpose. Tumor biopsy (primary or metastatic tumor) will be collected whenever possible during the treatment period.

Tumor samples remaining after analysis will be stored for up to 10 years after the end of the study and then destroyed, unless other time limitations are required by local regulations or ethical requirements. Tumor tissue samples should be fixed by formalin at site and will be shipped to the sponsor or its designee during or at the end of the study as requested by the sponsor.

Testing of biologic and/or tumor tissue samples may include but is not limited to the following tests;

- Growth factors; EGFR, VEGFR, HER2, c-MET
- Cytokines
- Cell cycle regulators, apoptosis-associated factors
- miRNAs; Let-7g, miR-433, miR-214, miR-21
- Epigenetic alterations, Genetic polymorphisms

#### 5.4.4. Pharmacokinetics

Pharmacokinetic parameters ( $C_{max}$ ,  $T_{max}$ , AUC, half-life, etc.) will be evaluated for apatinib. Blood samples for determination of plasma PK profiles of apatinib will be collected during the study per the time table below. The allowed time window for sampling is  $\pm 10$  minutes.

Time Point	Sample Number	Time (h)
Cycle 1/Day 1	1	Predose
	2	3–4 h postdose ( $T_{max}$ )
Cycle 1/Day 15	3	Predose on Day 15
	4	0.5–1 h postdose
	5	3–4 h postdose ( $T_{max}$ )
	6 (from 20±5% of patients)	8–12 h postdose
Cycle 2/Day 1 – Cycle 9/Day 1*	7–14*	Predose only (trough)

\* or until drug discontinuation or study completion

For PK sample for each pharmacokinetic evaluation, a total of 5~10 mL of blood will be collected at each time point. Collection, handling and storage of blood samples for determination of plasma PK profiles of apatinib will be explained in the study instructional manual.

## 6. CRITERIA FOR STUDY DISCONTINUATION OR SUBJECT WITHDRAWAL

### 6.1. Early Termination of the Study

The study may be terminated at any time by the sponsor for any reason. Some reasons may be due to new safety information, non-compliance issues, or judgment of study futility. In this event, the sponsor will inform the study Investigators, investigational sites, and all regulatory authorities. The extension period of the study may be terminated by the sponsor for any reason.

### 6.2. Criteria for Treatment Discontinuation

Subjects may voluntarily withdraw their consent from the study or the investigator may terminate a subject's participation if the investigator judges that the subject can no longer fully comply with the study requirements or if any of the study procedures are deemed potentially harmful to the subject.

If any of the following criteria is met during the treatment period, the study treatment will be discontinued.

1. Subject withdraws his/her consent.
2. The development of disease progression is confirmed according to the RECIST guideline (version 1.1) that makes it inappropriate to continue with study treatment according to the investigator's discretion or consent for continued treatment beyond RECIST confirmed disease progression is not obtained. (see [Section 6.3](#))
3. Clinical symptoms determined to be due to disease progression that makes it inappropriate to continue with study treatment according to the investigator's discretion or consent for continued treatment beyond clinical symptoms that are determined to be due to disease progression is not obtained. (see Section 6.3)
4. Onset of CTCAE grade  $\geq 3$  hypertension for which a causal relationship to the investigational product cannot be ruled out. (However, the judgment on whether or not to continue the treatment will be made by the investigator.)
5. Not having received a dose of the investigational product within the past consecutive 3 weeks for specific reasons, such as the onset of a treatment related adverse event.
6. Treatment with prohibited concomitant medication of sufficient dose and duration to confound the study results or to make continuation or restarting of treatment within 3 weeks unsafe for the patient.

7. Intolerable toxicity even after 2 dose reductions.
8. Confirmed positive pregnancy test.
9. The subject is lost to follow-up.
10. The subject is dead.
11. The investigator determines that continuation of study treatment is not appropriate.

### **6.3. Treatment continuation after disease progression**

Patients who will be treated beyond disease progression must review and sign a supplemental informed consent form before continuing on study drug. In addition, the following activity must be performed and the investigator must provide documentation of their opinion with supporting laboratory evaluation data that:

- The patient demonstrates investigator-assessed potential for clinical benefit and does not have rapid disease progression.
- It is safe to continue study drug and the patient, by evidence of signing consent, is tolerant of any continuing adverse events.
- ECOG performance status of 0 or 1 or stable ECOG performance status of 2 with no signs of rapid deterioration (ECOG status of 2 for past three months or more where the investigator feels that the deterioration of ECOG performance status from baseline at study entry is not indicative of potential to have serious adverse events within at least 30 days from beginning of continuation study treatment).
- The patient has a life expectancy of more than 30 days.
- Treatment beyond progression will not delay an imminent intervention to prevent serious complications of disease progression (e.g., CNS metastases).
- A radiographic assessment/scan should be performed approximately 8 weeks ( $\pm 7$  days), or earlier if the patient is exhibiting symptoms that may indicate continued progression, after initial Investigator-assessed progression to determine whether there has been a decrease in the tumor size or continued progressive disease. The assessment of clinical benefit should be balanced by clinical judgment as to whether the patient is clinically deteriorating and unlikely to receive any benefit from continued treatment with study therapy.

For the patients who continue receive study therapy beyond progression, further progression is defined as an additional 15% increase in tumor burden from time of initial progression. This includes an increase in the sum of diameters of all target lesions and/or the diameters of new measurable lesions compared to the time of initial progression or

rapid deterioration in the performance status. Study treatment should be discontinued permanently upon documentation of further progression.

Laboratory tests will continue with other study evaluations as described in the subsequent cycle study schedule to adequately ensure subject safety and further evaluations to ensure the subjects safety and continued benefit may be performed at the investigator's discretion.

After the decision to end study treatment permanently, an end of treatment (EOT) examination will be performed (at completion/discontinuation) and the subject will proceed to the post-treatment follow-up and survival follow-up. However, subjects in either treatment group will be withdrawn from the study if they meet any of the following criteria:

1. Subject withdraws his/her consent on the follow-up period.
2. Subject is lost to follow-up.

Post-treatment follow-up can be carried out before withdrawal if the subject agrees to it. Data that have already been collected on withdrawn subjects will be retained and used for analysis but no new data will be collected after withdrawal. When subjects withdraw from the study, they will be asked whether the study center can continue to contact them or family members for survival status only. If this consent is withdrawn, publicly accessible records may be used for documentation of death.

#### **6.4. Handling Early Withdrawals**

In any case of early withdrawal from the study, the date and reason should be recorded in the subject's eCRF and source documents. If the reason for early withdrawal was an AE, the outcome of the AE should be reported according to Section 7.2 and 7.3. All subjects who have received at least one dose of IP should complete all tests scheduled for the EOT wherever possible.

Screening numbers and randomization numbers, once allocated, cannot be reused. Any new subject will always receive new subject numbers (screening number and randomization number).

#### **6.5. Medical Care After the End of Treatment for Withdrawn Subjects**

Subjects for whom the study is terminated or suspended or who are withdrawn from the study due to disease progression or intolerable toxicity will be provided with or directed

to medical care and treatment, as deemed best for the study by the investigator.

After being withdrawn from the treatment, subjects will be monitored for survival status (See Section [3.4.5](#) and [3.4.6](#)).

## 7. SAFETY REPORT

### 7.1. Definition

#### 7.1.1. Adverse Event (AE)

An adverse event (AE) is defined as any untoward medical occurrence in a patient who has signed the informed consent form. The event need not necessarily have a causal relationship with the investigational product.

Examples of AEs include but are not limited to:

- Abnormal test findings that are clinically significant.
- Clinically significant symptoms and signs.
- Clinically significant changes in physical examination findings.
- Signs or symptoms resulting from drug overdose, misuse, or withdrawal.

Disease progression assessed by measurement of malignant lesions on imaging studies should not be reported as an AE. Treatment-emergent adverse event (TEAE) is defined as an AE that has a start date on or after the first dose of the investigational product until the final subject visit or, if it has a start date before the date of the first dose of study drug, increase in severity on or after the date of the first dose of investigational product until the final subject visit. The safety analysis will be carried out with TEAE. Adverse events collected during screening period (from the time of informed consent until right before the first administration of the investigational product) will be separately listed and reviewed.

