#### 7.1.2. Serious Adverse Event (SAE)

A serious adverse event (SAE) is any untoward medical occurrence that:

- Results in death.
- Is life-threatening.
- Requires inpatient hospitalization or prolongation of existing hospitalization.

- Results in persistent or significant disability/incapacity.
- Results in a congenital anomaly/birth defect.

 This does not include any of the following:

- Hospitalization or prolongation of existing hospitalization for a procedure (e.g., surgery, examination) that had been planned before the study
- Hospitalization or prolongation of existing hospitalization for follow-up observation of an already healed or improved condition
- Hospitalization or prolongation of existing hospitalization for examination or education
- Hospitalization or prolongation of existing hospitalization for non-medical reason (e.g., temporary absence of a family member)
- Admission to a hospice facility, nursing care facility, or rehabilitation facility

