5.9 Safety Variables

5.9.1 Adverse Events

An adverse event (AE) is defined as any untoward medical occurrence in a subject who has signed the informed consent form. The event need not necessarily have a causal relationship with the investigational product.

Examples of AEs include but are not limited to:

- Abnormal test findings that are clinically significant.
- Clinically significant symptoms and signs.
- Clinically significant changes in physical examination findings.
- Signs or symptoms resulting from drug overdose, misuse, or withdrawal.

Disease progression assessed by measurement of malignant lesions on imaging studies should not be reported as an AE.

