8.2.1 Overall Summary of Adverse Events

The number of subjects, incidence rate with its 95% CI and number of events will be presented for TEAEs, adverse drug reaction (ADR) and serious adverse event by treatment group during the study. Chi-square test or Fisher's exact test will be used for comparison of AE incidence between groups.

Data will be summarized in the following tables.

- *Table. Overall Summary of TEAEs – Safety Set*

- *Table. Overall Summary of Serious TEAEs – Safety Set*

- *Table. Overall Summary of ADRs – Safety Set*

- *Table. Overall Summary of Serious ADRs – Safety Set*

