8.2.3 Death and Serious Adverse Events and Other Significant Adverse Events

For Serious adverse events (SAEs, Sec 5.6.3), AEs leading to IP discontinuation and AEs leading to death, separate listings and summaries of subject counts and percents together with the number of events will be presented by treatment group and by SOC and PT. Also, subjects who died and primary reason of death will be summarized with counts and percents by treatment group.

Data will be summarized in the following tables and lists.

- *Table. Incidence of Serious TEAEs by SOC and PT – Safety Set*
- *Table. Incidence of Serious ADRs by SOC and PT – Safety Set*
- *Table. Incidence of TEAEs Leading to IP Discontinuation by SOC and PT – Safety Set*
- *Table. Incidence of ADRs Leading to IP Discontinuation by SOC and PT – Safety Set*
- *Table. Incidence of TEAEs Leading to IP Dose Reduction/Interruption by SOC and PT – Safety Set*
- *Table. Incidence of ADRs Leading to IP Dose Reduction/Interruption by SOC and PT – Safety Set*
- *Table. Incidence of TEAEs Leading to Fatal Outcome by SOC and PT – Safety Set*
- *Table. Incidence of ADRs Leading to Fatal Outcome by SOC and PT – Safety Set*
- *Table. Death Summary – Safety Set- List. Subjects with Serious TEAEs – Safety Set*
- *List. Subjects with Serious TEAEs – Safety Set*
- *List. Subjects with TEAEs Leading to IP Discontinuation – Safety Set*
- *List. Subjects with TEAEs Leading to IP Dose Reduction/Interruption – Safety Set*
- *List. Subjects with TEAEs Leading to Fatal – Safety Set*

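### The between-arm comparison of serious TEAEs has no version without cancer progression, so progression events can dilute or distort it in either direction

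*Protocol*

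**What the plan says.** Protocol 7.1.1 counts any untoward occurrence after consent as an AE: "The event need not necessarily have a causal relationship with the investigational product". It makes one exception for the cancer itself: "Disease progression assessed by measurement of malignant lesions on imaging studies should not be reported as an AE". SAP 5.9.1 carries over the same exception ("Disease progression assessed by measurement of malignant lesions on imaging" studies) and adds nothing on clinical progression or cancer death.

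Protocol 7.1.2 says that "A serious adverse event (SAE) is any untoward medical occurrence that" meets one of the listed outcomes, the first of which is "Results in death". Its listed exceptions all concern hospital or facility admissions. None concerns progression.

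The protocol does recognise progression that is not measured on a scan. Item 3 of section 6.2 is a separate discontinuation criterion: "Clinical symptoms determined to be due to disease progression that makes it inappropriate to continue with study treatment". No AE rule goes with it.

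In SAP 8.2.1, TEAEs, ADRs and serious events are summarised by arm, and a chi-square or Fisher's "exact test will be used for comparison of AE incidence between groups". SAP 8.2.3 lists serious and fatal tables by arm, among them "Incidence of TEAEs Leading to Fatal Outcome by SOC and PT", the corresponding ADR tables, and a Death Summary by primary reason. No listed table leaves out progression.

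**The concern.** The primary efficacy event in this trial is death, in a population where most deaths can be expected to come from the cancer. If cancer deaths and symptomatic progression are also recorded as serious TEAEs, the overall serious-TEAE comparison adds two things together: toxicity caused by the drug and the course of the disease.

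If progression events are equally common in both arms, they dilute a true excess of drug toxicity. If apatinib delays progression, fewer progression events on drug offset its toxicity. If progression events are recorded more often on drug, for example because treated subjects stay longer in the AE window, toxicity is overstated. In each case a reader of the summary row cannot tell which part moved.

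**Working it through.** **Is there a gap in the text?** The rules line up as follows.

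- Progression measured on imaging: not an AE (Protocol 7.1.1, SAP 5.9.1).
- Progression shown by symptoms: recognised in Protocol 6.2 item 3, with no AE exemption. Section 5.3.1 collects new or worsened signs, symptoms and disease.
- Untoward occurrence leading to death: serious (7.1.2), with no exemption for cancer.
- Window: 28 days after the last dose in Protocol 5.3.1, but up to the subject's last visit in Protocol 7.1.1 and SAP 5.9.2. Cancer deaths after the window count for OS only.

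Nothing elsewhere in either document closes the gap.

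**The plan's own figures.** The documents give no expected rate of serious or fatal TEAEs, so there is nothing on this point to reproduce. The OS design does reproduce: HR 0.72, 2:1 allocation and two-sided 5% give (1.960 + 0.842)² / [(2/3)(1/3)(ln 0.72)²] = 328 deaths for 80% power, against 325 stated. It has no bearing here.

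**Inputs for the dilution check.**

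- Arm sizes: 459 at 2:1 gives 306 v 153, taken as the safety set.
- Level: two-sided 5%.
- Drug-caused serious events: 12% apatinib v 4% placebo (assumed).
- Progression-related serious events: varied (assumed).

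**Formulas.** With the two kinds of event independent within a subject, the total is p = 1 − (1 − drug)(1 − progression). Power is Φ[(|d| − 1.96·s₀)/s₁] plus the small opposite tail. Here d is the difference, s₀ = √[p̄(1 − p̄)(1/153 + 1/306)] with p̄ the pooled rate, and s₁ = √[p_P(1 − p_P)/153 + p_A(1 − p_A)/306].

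Example with 30% progression events in both arms. Placebo: 1 − 0.96 × 0.70 = 32.8%. Apatinib: 1 − 0.88 × 0.70 = 38.4%. Then d = 0.056, s₀ = 0.0477, s₁ = 0.0470, and power is Φ(−0.80) ≈ 21%.

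| Progression events, placebo v apatinib | All serious, placebo v apatinib | Difference (points) | Risk ratio | Power |
|---|---|---|---|---|
| none | 4.0% v 12.0% | 8.0 | 3.00 | 83% |
| 10% v 10% | 13.6% v 20.8% | 7.2 | 1.53 | 46% |
| 30% v 30% | 32.8% v 38.4% | 5.6 | 1.17 | 21% |
| 45% v 45% | 47.2% v 51.6% | 4.4 | 1.09 | 14% |
| 30% v 25% | 32.8% v 34.0% | 1.2 | 1.04 | 6% |
| 30% v 35% | 32.8% v 42.8% | 10.0 | 1.30 | 54% |

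In the last row the observed difference exceeds the true drug difference of 8 points, so the direction is not fixed.

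**Other assumed rates.** With 15% v 5%, power is 92% without progression. It is 62%, 42%, 30% or 23% with progression events in 10%, 20%, 30% or 40% of both arms, and the risk ratio falls from 3.0 to between 1.62 and 1.14. With progression in 40% of placebo and 30% of apatinib subjects, the ratio is 0.94. For fatal events, 4% v 1% (ratio 4.0) becomes a ratio of 1.12 once 20% cancer deaths are added to both arms.

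**Are such backgrounds plausible?** Protocol 1.2 cites OS of 4.7 and 6.5 months and PFS of 1.8 and 2.6 months (placebo, apatinib) from the Chinese phase III study. If the OS figures are treated as medians with constant hazards, deaths in the 28 days after stopping are 1 − exp(−(ln 2/OS) × 28/30.44), or 12.7% and 9.3%. Deaths before progression add at most PFS/OS, or 38% and 40%. Combining the two gives 0.383 + 0.617 × 0.127 = 0.46 and 0.400 + 0.600 × 0.093 = 0.46. This is only a rough ceiling. It equates treatment time with PFS, although Protocol 6.3 allows treatment beyond progression, and it covers deaths only. The protocol also labels the OS figures as means, which would raise the 28-day share.

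**The case against.** The strongest reply is that much of the separation is already planned. SAP 8.2.3 tabulates serious and fatal TEAEs by SOC, PT and arm, so events coded as progression have their own rows and other terms can be compared with placebo beside them. The toxicities that the documents name (hypertension, proteinuria, hand-foot syndrome) have distinct terms. The Death Summary separates deaths by primary reason and by arm. No hypothesis, power target or decision rule rests on the overall test, and the fatal table has no stated test. The IDMC has two planned safety reviews. The AE rule also has a coherent reading: lesion growth on a scan is not an AE, while symptoms are, scan or no scan. The eCRF completion guidance and table shells are not available, so actual coding practice is unknown.

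All of this stands as mitigation, but none of it supplies the missing comparison. A subject with both a progression event and a toxic event appears in two PT rows, so subject-level incidence without progression cannot be obtained by subtracting rows. The Death Summary does not cover non-fatal serious events. The ADR tables rest on investigator causality rather than on randomisation. The SAP also defines ADR in two ways: section 5.9.4 includes events judged unlikely to be related and section 8.2 leaves them out. Under 5.9.4 the filter removes little.

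A reader might also infer that the remedy is to exempt clinical progression from AE reporting. The documents do not support that. It would stop attributed symptoms from being collected at all, in a trial whose exclusion criteria flag bleeding risk with this drug class. Broad collection with later sorting is defensible.

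**Conclusion.** The gap is real. The all-cause serious-TEAE comparison in SAP 8.2.1 can mix cancer progression with drug toxicity, and no planned output shows the subject-level comparison without it. With drug-caused serious events of 12% v 4%, 306 v 153 subjects and independence within subjects, power falls from 83% to 46%, 21% or 14% at progression rates of 10%, 30% or 45% in both arms. These rates are assumptions and the documents give none.

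Two stronger readings are tempting. One is that progression makes up the bulk of the safety comparison. No event rates support that, and a possibly large share is as far as the documents go. The other is that the plan hides toxicity. Masking is possible, but overstatement is possible too, and the by-arm PT tables and the Death Summary limit both.

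**What to change.** In SAP 8.2.1 and 8.2.3, add two outputs:

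- the overall serious-TEAE comparison after excluding preferred terms for progression of the study cancer;
- the fatal-TEAE table with the same exclusion.

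Fix the term list at the blinded meeting that SAP 4.4 and 6.2 already place before database lock. Keep the all-events tables beside the new ones, and leave AE collection in Protocol 7.1.1 and SAP 5.9.1 unchanged.

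The cost is a few tables, one short list and a sentence or two in the SAP. There are two downsides. A drug-caused event mis-coded as progression drops out of the added tables, which is why the all-events tables must stay. Progression symptoms coded under other terms remain in the added tables, so the full 83% is not recovered. For example, if the list reduced a 30% background to 10% in both arms, power would rise from 21% to 46%.
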